For evaluation of response to treatment (primary endpoint), perform MRI 4-6 months after each HEC. **Except in the case of bilobar disease (for which 2 sessions of HEC should be scheduled upfront), retreatment (new HEC treatment) will be performed according to follow-up MRIs.** An MRI will be performed 4 to 6 weeks after each chemoembolization treatment. In case of tumor remnant or recurrence treatable by HEC (i.e., no portal trunk thrombosis or in a territory ≥ 3 segments, hepatopoitic portal flow, WHO status < 2 , no hepatic decompensation, no extrahepatic metastasis), a new course of HEC should be performed targeting the remnant or recurrence (same distinction as above: supra-selective OR lobar approach). In the absence of tumor remnant or recurrence on MRI performed 4-6 weeks, MRI surveillance is performed every 3 months and the modalities of retreatment are the same as before.

In all cases, MRI at 6 months from the date of inclusion must be performed (primary endpoint of the study).

At the end of the session, embolization with additional material is not recommended.

If in case of a single HEC, a recurrence of the disease is observed at the 3-month MRI, a second HEC can be performed and will be performed as part of the protocol.

V.3 Premedication and concomitant treatments

Sufficient hydration (up to 2 liters per day), adapted to the cirrhotic context, will be prescribed before and after chemoembolization for at least 48 hours.

In case of nausea or vomiting, provide adequate treatment according to center procedures.

After the procedure, level 1 to 3 (WHO) analgesics will be used in an appropriate dose.

At the end of the procedure, the pain felt by the patient will be recorded using a visual analog scale (VAS rated from 0 to 10). If VAS > 3, titration of IV morphine by an IDE according to the recommendations.

Any treatment required for patient comfort will be prescribed at the discretion of the investigator. The use of a preventive anti-emetic treatment is recommended.

VI. EXPECTED TOXICITIES AND DOSE ADJUSTMENT

VI.1 Chemoembolization

The main adverse effects expected with chemoembolization are:

- Unwanted reflux or passage of microbeads into normal arteries adjacent to the targeted lesion or through the lesion to other arteries or arterial beds
- Non-targeted embolization
- Pulmonary embolization
- Ischemia in an undesired location
- Capillary bed saturation and tissue damage
- Rupture of a vessel or lesion and hemorrhage

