- Neurological deficits including cranial nerve palsy
- Vasospasm
- Deaths
- Re-permeabilization
- Foreign body reactions requiring medical intervention
- Infection requiring medical intervention
- Catheter tip clot formation and subsequent mobilization

Expected effects related to the embolization procedure (from CNIHM anticancer files November 2008)

- Fever, hypochondrial pain, vomiting
- Transient thrombocytopenia and liver dysfunction
- Increased transaminases (cytolysis)
- Local ischemic and septic manifestations (cholecystitis, hepatic infarction, hepatic abscess, digestive hemorrhage)
- Renal insufficiency
- Hematoma at the puncture site
- Acute lower limb ischemia

Adaptation for chemoembolization

The interval between chemoembolization sessions should be 6 weeks plus or minus 1 week. Any additional time must be agreed upon by the coordinator.

HEC Session Rehearsal:

The chemoembolization session(s) are scheduled every 6 weeks, plus or minus 1 week.

The imaging technique, after each session, will be MRI and a cone beam CT acquisition (after 1^{ière} HEC for the translational study and after, if possible, each HEC to assess the quality of chemoembolization).

Subsequent sessions will be performed according to tumor response. No additional session is recommended in case of complete tumor response according to the modified RECIST criteria (mRECIST) (Appendix 2) or progression of a previously chemoembolized tumor.

In case of non-hematological toxicity of grade 3 or 4 attributable to HEC, no additional HEC is performed. In case of bleeding and/or severe liver failure and/or other toxicities secondary to a grade ≤ 3 chemoembolization session, the next session(s) will be performed at the discretion of the investigator.

Transient increases in ALT and/or AST in the 24-48 hours after HEC do not lead to failure to perform additional HEC. Indeed, this transient increase does not have a significant impact (R Sacco et al, Clinical impact of selective transarterial chemoembolization on hepatocellular carcinoma: A cohort study. World J Gastroenterol 2009 April 21; 15(15): 1843-1848).

VI.2 Idarubicin

The main effects expected for idarubicin (Zavedos® powder for solution for infusion) according to the current versions of the SPCs (version of 6/07/2006 appendix 8) are the following

- Significant spinal cord hypoplasia which can be responsible for serious or even fatal conditions
- Alopecia reversible on discontinuation of treatment

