An anonymized copy on CD ROM (present in each observation book) of each morphological evaluation until progression (even if beyond 6 months) (MRI) is to be made. The copies will be sent to the CRGA of the FFCD for centralized review .

For the translational study, perform a cone beam CT acquisition or a hepatic CT scan without injection at the time of the 1^{ère} HEC.

For the clinical study, if possible, perform a cone beam CT acquisition at each HEC to assess the quality of the chemoembolization.

VII.3 Post-treatment monitoring beyond 6 months after inclusion:

After the end of chemoembolization treatment, patients will be followed according to TNCD recommendations:

Clinical and biological evaluation every 3 months for the first year and then every 6 months for 1 year:

- Clinical examination (weight, WHO)
- Biological tests: liver tests (ASAT, ALAT, GGT, bilirubinemia, albuminemia, TP)
- Marker : AFP

Morphological assessment:

- Chest CT scan without injection, every 6 months for 2 years
- Hepatic MRI (or CT scan) - liver ultrasound by a trained operator alternating every 3 months for 2 years

Monitoring data will be collected in the observation book during this 2-year period.

VIII. STOP PROCESSING THE STUDY

The processing of the study will be stopped in case of:

- Investigator's decision
- Major toxicity requiring discontinuation of treatment
- Serious or unexpected event requiring discontinuation of protocol treatment
- Progression of the disease
- Patient refusal or withdrawal of consent
- Death of the patient

In all cases of treatment discontinuation, the patient remains in the analysis for intention-to-treat and overall survival, and for 30 days after the last study treatment for toxicity.

There is no exclusion period for a subsequent therapeutic trial.

IX. TRANSLATIONAL STUDY

Only patients who have signed their translational-biological informed consent will be collected. Rationale for the study (see Appendix 15).

Blood sampling for VEGF determination

- 4 sampling times:

After the 1^{ière} HEC at D0, D1, D2 and D3

- Samples :

At each sampling time (4 times), collect 2 x 7 ml EDTA tubes of blood.

Centrifuge the blood tubes at room temperature at 1000 g for 15 minutes.

Collect the plasma to be distributed in a minimum of 4 cryotubes (minimum 1 mL per cryotube).

Identify the cryotubes with the patient's initials + inclusion number in the study, the sampling times.

Freeze the 2 plasma cryotubes at -20°C then at -80°C.

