- The rate of patients in objective response** (complete response or partial response) at 6 months according to mRECIST criteria and evaluated by the investigator.
- The rate of patients in objective response** (complete response or partial response) at 6 months according to EASL criteria assessed by the investigator and in centralized review.

- Time to treatment failure

It is defined as the time interval between the date of inclusion and the date of protocol treatment failure. Death, progression, and any discontinuation of protocol treatment (regardless of cause) are considered treatment failures.

Patients alive without failure will be censored at the date of the last 6-month morphological evaluation.

- The best response according to the mRECIST criteria

- Progression-free survival

It is defined as the time interval between the date of inclusion and the date of 1st progression according to mRECIST criteria (assessed in centralized review) or death (regardless of cause).

Patients living without progression will be censored at the date of last news.

- Overall survival

It is defined as the time interval between the date of inclusion and the date of death (regardless of cause) or the date of last news for living patients.

- Tolerance of the treatment

Toxicities will be evaluated by the NCI-CTC v4.0 criteria. They will be described according to their grade in terms of number of toxicities and number of patients who experienced the toxicity.

- Quality of life (QLQ-C30 questionnaires and its HCC18 module specific to HCC)

XII.3 Calculation of the number of subjects needed

The assumptions are:

- H0: A proportion of patients with an objective response at 6 months of 25% or less is not acceptable
- H1: A proportion of patients with an objective response at 6 months of more than 25% would demonstrate the effectiveness of the treatment. A rate of 40% is hoped for.

Using a 2-stage Fleming design (Fleming, 1982) with a one-sided alpha risk of 5% and power of 90%, it is necessary to include **86 treated and evaluable patients**.

At the 1^{ère} stage: 43 patients will be included

- If 10 or fewer patients have an objective response, the trial will be stopped for futility (H1 rejection)
- If 18 or more patients have an objective response, the trial will be stopped for efficacy (rejection of H0)

If not, we will go to 2^{ème} step including 43 additional patients

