### **7.4.3 Time to treatment failure**

#### **7.4.3.1 Definition**

It is defined as the time between the date of inclusion and the date of definitive cessation of treatment or death (whatever the cause). Patients without definitive treatment discontinuation and not deceased will be censored at the date of their last HEC.

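### SAP time to treatment failure does not follow the protocol definition: progression is no longer an event in its own right, and living patients are censored at their last chemoembolization

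*SAP*

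**What the plan says.** Protocol XII.2.2 measures time to treatment failure from inclusion to failure of the protocol treatment. The events are listed: "Death, progression, and any discontinuation of protocol treatment (regardless of cause) are considered treatment failures". The censoring rule follows: "Patients alive without failure will be censored at the date of the last 6-month morphological evaluation".

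SAP 3.1.2 carries the endpoint over under the same name. SAP 7.4.3.1 (the time-to-treatment-failure section; the number is used again for overall survival) has two events, definitive cessation of treatment and death from any cause. Its censoring rule is: "Patients without definitive treatment discontinuation and not deceased will be censored at the date of their last HEC". HEC is the documents' abbreviation for a chemoembolization session. SAP 7.4.3.2 then plans Kaplan-Meier medians and rates with 95% confidence intervals. The SAP text gives no reason for either difference.

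Three protocol rules bear on the comparison:
- Section VIII lists "Progression of the disease" among the reasons for stopping study treatment.
- Section VI.1 says: "No additional session is recommended in case of complete tumor response". The same sentence says so too for progression of a tumor already chemoembolized.
- Section V.2.3 says that if recurrence is seen at the 3-month MRI after a single session, "a second HEC can be performed and will be performed as part of the protocol".

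**The concern.** Two definitions share one name. The SAP does not name progression, so a patient who progresses after the last session may never count as a failure. The censoring date also moves from an imaging visit, which the protocol requires at six months whatever the timing of treatment, to a treatment date that is usually much earlier.

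At stake is what the reported median and rates mean. They would carry the protocol's label while depending on how sites record the end of treatment. The SAP's double programming (8.2.2) would not catch this, because both statisticians would program the same definition.

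**Working it through.** The documents give no figure for this endpoint, so there is none to reproduce. The check compares the definitions case by case, then works out the censoring dates.

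**Step 1. The same patient under each rule.**

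| Situation | Protocol XII.2.2 | SAP 7.4.3.1 |
|---|---|---|
| Death as first event | Event | Event |
| Progression during treatment, treatment stopped | Event at progression | Usually an event, dated at cessation |
| Progression after the last session, alive, no cessation recorded | Event at progression | Censored at the last session, before the progression |
| Recurrence at the 3-month MRI, retreated, if it meets mRECIST progression | Event | No event while treatment continues |
| Alive, no progression, no cessation recorded | Censored at the 6-month evaluation | Censored at the last session |
| Planned completion, or stop for complete response | Not stated | Not stated |

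**Step 2. When the last session falls.** Inputs:
- first session at most 2 weeks (14 days) after inclusion (Protocol IV);
- 1 to 4 sessions, 6 weeks plus or minus 1 apart, so 35 to 49 days (SAP 4.2, Protocol VI.1);
- duration = difference in days + 1, and 1 month = 30.4375 days (SAP 6.2);
- for the earliest case, I assume the first session takes place on the day of inclusion.

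For k sessions, earliest = 35(k-1) + 1 days and latest = 14 + 49(k-1) + 1 days.

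| k | Earliest | Latest | Months before a 6.00-month evaluation |
|---|---|---|---|
| 1 | 1 d = 0.03 mo | 15 d = 0.49 mo | 5.51-5.97 |
| 2 | 36 d = 1.18 mo | 64 d = 2.10 mo | 3.90-4.82 |
| 3 | 71 d = 2.33 mo | 113 d = 3.71 mo | 2.29-3.67 |
| 4 | 106 d = 3.48 mo | 162 d = 5.32 mo | 0.68-2.52 |

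A patient with one session, a complete response and no recorded cessation therefore contributes at most 0.49 months under the SAP, against about 6 under the protocol. These are regular-schedule dates and do not bound every case. Protocol V.2.3 allows retreatment after surveillance MRI, and VI.1 allows longer intervals ("Any additional time must be agreed upon by the coordinator"). The last session can then fall at or after six months.

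**Step 3. Why the censoring is informative.** Take two patients with the same treatment dates, both alive at six months and neither with a recorded cessation. One dies later, during follow-up; the other is alive at the analysis. Under the SAP the first stays in the risk set until death. The second is removed back at the last session. Whether a patient is at risk at a given month thus depends on what happens after it, contrary to the Kaplan-Meier assumption. Under the protocol rule both remain at risk up to the 6-month evaluation.

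**Step 4. Direction.** Progressions left uncounted raise the estimated failure-free rate. Removing survivors early while keeping patients who later die lowers it. Recording an end of treatment for everyone removes nearly all censoring and brings failures forward. The documents give no progression rates, cessation rates or recording rule, so the net effect has no determinable size or sign.

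**The case against.** The best defence is that progression is not really lost. Protocol VIII stops study treatment for progression, and VI.1 recommends no further session when a treated tumor progresses. Progression during treatment will therefore normally reach the SAP endpoint as cessation. This stands, and it narrows the point: the loss is mainly progression found after the last session without recorded cessation. The retreated recurrence in V.2.3 is a conditional case. If such a recurrence does meet mRECIST progression, the tension is between V.2.3 and VIII of the protocol, which must be reconciled there; the SAP did not create it.

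A second defence is that the protocol definition is loose too. It counts discontinuation from any cause without saying whether finishing the planned sessions, or stopping for complete response, is discontinuation. This also stands. A reader might infer that, if an end of treatment is recorded for everyone, the SAP rule breaks down while the protocol rule holds. The documents do not support that: if completion counts as discontinuation, the protocol's version behaves almost the same way. Any numerical comparison must code completion identically under both.

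The protocol's censoring phrase is also awkward in translation. It nevertheless refers to an imaging evaluation and cannot mean the last session.

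Lastly, the endpoint is descriptive, in a single-arm trial, and progression-free and overall survival report progression and death directly. This limits the consequence but does not remove the mismatch.

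**Conclusion.** The SAP definition is wrong as written, for one descriptive secondary endpoint. It differs from the protocol in its named events and its censoring date, without a stated reason. Its censoring is informative wherever living patients have no recorded cessation. On the regular schedule the censoring date comes 0.68 to 5.97 months before a 6.00-month evaluation, depending on the number and spacing of sessions. That range assumes on-time sessions and no retreatment after surveillance imaging.

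Three stronger readings go beyond the documents. A reader might infer that progression is removed altogether; sections VI.1 and VIII show that it is not. A reader might infer a bias of known size or in favor of the treatment; opposing effects and missing rates rule that out. Because SAP 4.6.1 already reports the interim result, a reader might also infer that the definition was changed in light of the data; the documents do not show when or why it changed.

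The primary endpoint, the stopping decision, progression-free survival and overall survival are unaffected. The textual mismatch is certain; its numerical effect is unknown.

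**What to change.** In SAP 7.4.3.1:

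1. Restore the protocol's events: the first of progression, death or discontinuation of protocol treatment.
2. Censor patients alive without failure at the 6-month morphological evaluation. If that scan is missing, a case SAP 5.1.2 already expects, use the last available morphological evaluation before it.
3. Define the discontinuation event and its date. State, consistently in both documents, whether planned completion and stopping for complete response are failures. This is a coding rule for the endpoint and leaves treatment decisions unchanged.
4. If the SAP definition is kept, justify it, report it under a different name, and report the protocol definition alongside.

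The cost is SAP wording, a clarifying line for the protocol definition, and reprogramming of one derived variable. Session, imaging, progression and death dates are already needed for other SAP analyses. The documents do not show whether a dated end of treatment is collected, so that must be checked first.

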- Digestive disorders: nausea, vomiting, diarrhea
- Stomatitis, esophagitis
- Elevated liver enzymes and bilirubin in 20-30% of cases
- Skin rash
- Acute heart rhythm disturbances, acute or late heart failure (rare before a cumulative dose of 93 mg/m²)
- Red coloration of the urine 24 to 48 hours after treatment.

As with other DNA altering anticancer agents, myelodysplastic syndromes and acute myeloid leukemias have been observed after combination therapy with anthracycline.

In case of idarubicin-related effects, no dose adjustment of idarubicin for loading the microbeads is planned. The chemoembolization session is then postponed or cancelled.

VII. MONITORING DURING AND AFTER TREATMENT

VII.1 Before each HEC

- Complete clinical examination: weight, vital signs, WHO general condition (which should be 0 or 1), pain assessment (VAS)
- Biological work-up: CBC/platelets, blood ionogram, creatinine, albumin, transaminases (AST, ALT), alkaline phosphatases (ALP), GGT, total and conjugated bilirubin, PT
- Adverse event evaluations of previous HECs according to NCI CTC version 4.0
- Quality of life questionnaires (QLQ-C30 and its module HCC18)

Prior to the session, the investigator should ensure that the patient has adequate hepatic and hematological function:

- Bilirubin ≤ 1.5 mg/dL, PNN $\geq 1,000/\text{mm}^3$, platelets $\geq 50,000/\text{mm}^3$, creatinine level $\leq 150 \mu\text{mol/L}$
- Hepatopoietic flow, thrombosis is considered significant if it involves at least 3 segments. The procedure is then contraindicated. A Doppler is strongly recommended before the embolization sessions to ensure that the procedure can be performed. It is recommended to evaluate these criteria according to the habits of the center.

For patients participating in the translational study: blood sampling for translational study (see paragraph IX)

VII.2 After each HEC

Hepatic MRI (or CT scan in case of contraindication to MRI) will be performed 4 to 6 weeks after each chemoembolization to assess their effectiveness.

Assessment imaging at 6 months from the date of inclusion MUST be performed regardless of the time of last HEC to assess the primary endpoint of the study.

Target measurements will be done according to mRECIST v1.1 to assess the primary endpoint of the study and according to EASL criteria to assess the secondary endpoint (Appendices 4 and 5).

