#### **4.2 Treatment arms**

[figure not shown]
There is a single study treatment arm consisting of 1 to 4 sessions of chemoembolization (sessions spaced 6 weeks +/- 1) with idarubicin-loaded microbeads (100-300 µm) (10 mg).

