## **6.2 Agreements concerning dates and durations**

Time since inclusion will be defined as the time elapsed since the day of inclusion, the day of inclusion being considered as day 1.

Time since start of treatment will be defined as the time elapsed since the day of the first treatment course, the day of the first treatment course being considered as day 1.

As a result, durations are calculated using the following rule, for example for the time elapsed between death and inclusion: day of death - day of inclusion **+ 1**.

The day preceding the day of inclusion (*resp.* the day preceding the day of treatment) will be considered as day -1 (day 0 does not exist).

The date of last news will default to the date of the last examination/monitoring performed.

The following conversion rules will be used to convert numbers of days into numbers of months or years:  
1 month = 30.4375 days; 1 year = 365.25 days.

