#### **7.4.3.2 Evaluation**

The time scale considered is the month.

Time to treatment failure will be plotted using the Kaplan Meier estimator. Median times and rates at different temporalities will be calculated, along with their 95% confidence intervals.

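### SAP 7.4.3.1 drops progression from the listed time-to-treatment-failure events and censors at the last chemoembolization, unlike protocol XII.2.2, and gives no reason

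*SAP*

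**What the plan says.** Protocol XII.2.2 defines time to treatment failure (TTF) from inclusion and names three kinds of failure: "Death, progression, and any discontinuation of protocol treatment (regardless of cause) are considered treatment failures". Its censoring rule is: "Patients alive without failure will be censored at the date of the last 6-month morphological evaluation". Protocol VII.2 secures that imaging for every patient: "Assessment imaging at 6 months from the date of inclusion MUST be performed regardless of the time of last HEC".

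SAP 7.4.3.1 also starts the clock at inclusion but ends it at "the date of definitive cessation of treatment or death (whatever the cause". For everyone else it states: "Patients without definitive treatment discontinuation and not deceased will be censored at the date of their last HEC". SAP 7.4.3.2 then promises: "Median times and rates at different temporalities will be calculated, along with their 95% confidence intervals".

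Three other protocol sections bear on the reading:
- Section VIII lists disease progression among the reasons to stop study treatment.
- Section VI.1 makes further sessions depend on tumor response. It recommends none after a complete response or after progression of a tumor already chemoembolized.
- Section V.2.3 allows a residual or recurrent tumor to be treated again by HEC within the protocol.

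**The concern.** Both halves of the endpoint changed between protocol and SAP: the list of events and the censoring date.

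The censoring change is the more serious. The last HEC is a treatment date, not the date on which failure status was last known. The trial requires imaging well beyond it, and the SAP's own rule for progression-free survival (7.4.2.1) censors at the last evaluation. Because further sessions depend on response, the date of the last HEC is also plausibly related to prognosis.

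At stake is whether the reported TTF median and rates describe the endpoint that the protocol named, and whether the curve can be interpreted at the later time points.

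**Working it through.** The plan states no figure for TTF (no assumed median and no sample size), so there is none to reproduce. The check compares the two definitions, works out the dates they imply, and adds an illustration.

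**1. The definitions side by side**

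| | Protocol XII.2.2 | SAP 7.4.3.1 |
|---|---|---|
| Death | event | event |
| Stopping treatment | any discontinuation | definitive cessation (not defined) |
| Progression | event | not listed |
| Censoring if no failure | 6-month morphological evaluation | last HEC |

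**2. Which progressions are lost**
- Progression followed by a recorded definitive stop: still an event, but dated at the stop.
- Progression that is retreated by HEC: not an event at that time.
- Progression after the last session with no recorded stop: not an event.

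The documents give no counts. Section V.2.3 speaks of residual tumor and recurrence; whether a given recurrence is mRECIST progression depends on an appendix not available here.

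**3. Why the censoring rule biases the estimate**

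Take two patients with the same history up to a last HEC at 1.87 months. One dies at 4 months and stays in the risk set until then. The other is failure-free at 6 months and is removed at 1.87 months. Membership of the risk set after the last HEC thus depends on what happens later, which Kaplan-Meier does not allow.

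**4. Censoring dates if finishing HEC without failing is not definitive cessation**

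Inputs:
- Start at day 0 to 14 after inclusion (protocol IV sets 2 weeks as the maximum).
- 1 to 4 sessions, 5 to 7 weeks apart (SAP 4.2).
- Duration in days = date difference + 1; 1 month = 30.4375 days (SAP 6.2).

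Formula: months = (start + gap × (sessions − 1) + 1) / 30.4375.

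| Sessions | Earliest (start 0, gap 35 days) | Latest (start 14, gap 49 days) | Discarded before 6 months |
|---|---|---|---|
| 1 | 1/30.4375 = 0.03 | 15/30.4375 = 0.49 | 5.51-5.97 |
| 2 | 36/30.4375 = 1.18 | 64/30.4375 = 2.10 | 3.90-4.82 |
| 3 | 71/30.4375 = 2.33 | 113/30.4375 = 3.71 | 2.29-3.67 |
| 4 | 106/30.4375 = 3.48 | 162/30.4375 = 5.32 | 0.68-2.52 |

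The last column is 6 minus each censoring time. Six months is 6 × 30.4375 = 182.6 days, and the latest planned date is day 162. On the planned schedule no failure-free patient is still at risk at 6 months. A postponed session or a late retreatment would move the date later.

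**5. The other reading**

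If any final end of HEC is definitive cessation, few patients are censored at the last HEC. A patient who stops because of complete response, as section VI.1 recommends, is then a treatment failure.

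**6. Illustration on assumed inputs**

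Assume exponential failure times with a median of 9 months, and 1/2/3/4 planned sessions in 25/40/20/15% of patients. The first session is at 0.25 months and later ones follow every 1.38 months. The true failure-free rate is 0.79 at 3 months and 0.63 at 6 months.
- Every failure up to 6 months counts, all others are censored at the last HEC: 0.70 at 3 months and about 0.00 just before 6 months.
- Only deaths (15% of first events) and progressions before the planned last session count, all others are censored at the last HEC: 0.79 and 0.63, with events in 27% of patients instead of 37%. Lost progressions raise the curve, discarded time lowers it, and here they offset each other. This agreement comes from the construction, in which being a death is unrelated to the time of failure.

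The two cases show why the net effect cannot be stated from the documents.

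**The case against.** The strongest reply has four parts.

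- **Progression has not disappeared.** A reader might infer from SAP 7.4.3.1 that it no longer counts at all. The documents do not support that: section VIII makes it a reason to stop treatment, so much of it may enter as cessation. This stands, and limits the loss to the last two groups in step 2.
- **The censoring dates hold under one reading only.** If finishing HEC is definitive cessation, the table in step 4 does not describe most patients. This stands too, but it does not rescue the rule, because it replaces early censoring with counting completed treatment, even after complete response, as failure.
- **A reason may exist elsewhere.** Some SAP pages were not available. The SAP's table of contents, however, lists no section on departures from the protocol.
- **Little depends on it.** TTF is descriptive, with no test or decision rule. This is correct and keeps the point at moderate weight.

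**Conclusion.** The point holds. SAP 7.4.3.1 departs from protocol XII.2.2 in its listed events and its censoring date, without a stated reason in the text available. The censoring rule is wrong as written under either reading of definitive cessation. The month ranges rest on the first reading and on sessions being given on schedule.

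The impact is confined to one descriptive secondary endpoint. The primary endpoint, the stopping decision, progression-free survival and overall survival do not use this rule.

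Two stronger inferences are not supported. One is that the reported curve must be too low, or too high: lost progressions and discarded failure-free time act in opposite directions, and the documents give neither the session mix nor the number of retreated progressions. The other is that the definition was changed in response to results. SAP 4.6.1 does report the January 2017 interim result (22 responders among 44 evaluable patients), so this text was written after that look. The documents do not show when the TTF definition was first changed, or why.

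**What to change.** In SAP 7.4.3.1, restore the protocol XII.2.2 definition: the event is the first of death, progression or any discontinuation of protocol treatment, and patients alive without failure are censored at the 6-month morphological evaluation.

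Add the following, labelled as additions to the protocol text:
1. Progression is by mRECIST, with the reader named; centralized review would match the progression-free survival definition.
2. Progression counts whether or not it is retreated by HEC.
3. Ending HEC because of complete response or completion of the planned sessions is not failure.
4. If the 6-month imaging is missing, censor at the last morphological evaluation without failure.

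The cost is one SAP paragraph and the TTF program. No new data are needed: progression dates are already required for progression-free survival, and the 6-month imaging for the primary endpoint.
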